9. SAFETY ANALYSES

All safety analyses will be based on the safety population.

9.1. Study Drug Exposure and Compliance

9.1.1. Number of Applications Applied

The Number of Applications Applied will be summarized by treatment using the following statistics: n, mean, standard deviation [SD], median, minimum and maximum.

9.1.2. Days of Exposure

Days of Exposure = (stop date of study drug - start date of study drug) + 1.

Days of Exposure will be summarized by treatment using the following statistics: n, mean, standard deviation [SD], median, minimum and maximum.

Also Days of Exposure will be summarized by treatment using the following categories:

- < 28 Days
- 28 to 56 Days
- 57 to 84 Days
- > 84 Days

9.1.3. Compliance

Compliance will be calculated for all subjects in the safety population.

Compliance (%) = $A/P \times 100$, where:

- A = Total number of applications actually applied.
- P = Total number of applications for the respective evaluation period.

Compliance will be summarized by treatment using the following statistics: n, mean, standard deviation [SD], median, minimum and maximum.

In addition, the number and percentage of subjects that have a compliance rate between 80% and 120% will be summarized by a Yes/No category. Note a subject is considered compliant with the dosing regimen if the subject has applied at least 80% but no more than 120% of the expected applications for the respective evaluation period.

9.2. Local Cutaneous Safety Evaluation

Non-lesional erythema, peeling, dryness, stinging, burning and itching scores will be summarized by treatment group and visit including sample size, frequency count and percentage for each visit. A similar summary will be provided excluding subjects with signs or symptoms present at Baseline.

Non-lesional erythema, peeling, dryness, stinging, burning and itching scores and their corresponding descriptions are listed in Table 7, Table 8, Table 9, Table 10, Table 11 and Table 12 respectively.

Table 7: Scoring of Non-Lesional Erythema

Severity	Score	Description
None	0	No erythema
Mild	1	Light pinkness present
Moderate	2	Definite redness, easily recognized
Severe	3	Intense redness

Table 8: Scoring of Peeling

Severity	Score	Description
None	0	No peeling
Mild	1	Barely perceptible shedding, noticeable only on light scratching or rubbing
Moderate	2	Obvious but not profuse shedding
Severe	3	Heavy scale production

Table 9: Scoring of Dryness

Severity	Score	Description
None	0	No dryness
Mild	1	Slight barely perceptible fine superficial scale
Moderate	2	Clearly perceptible fine scale giving skin a powdery appearance
Severe	3	Marked roughness, cracked skin with fissures

Table 10: Scoring of Stinging

Severity	Score	Description
None	0	No stinging
Mild	1	Slight sharp, tingling/stinging sensation; not really bothersome
Moderate	2	Definite sharp, tingling/stinging sensation; that
		is somewhat bothersome
Severe	3	Sharp, tingling/stinging sensation that has caused definite discomfort

Table 11: Scoring of Burning

Severity	Score	Description
None	0	No burning
Mild	1	Slight warm, burning sensation; not really bothersome
Moderate	2	Definite warm, burning sensation; that is somewhat bothersome
Severe	3	Hot, burning sensation that has caused definite discomfort

Table 12: Scoring of Itching

Severity	Score	Description
None	0	No itching
Mild	1	Slight itching; not really bothersome
Moderate	2	Definite itching that is somewhat bothersome, without loss of sleep
Severe	3	Intense itching that has caused pronounced discomfort; night rest interrupted and excoriation of the skin from scratching may be present

Overall cutaneous tolerance was graded at the Week 12 visit, or the last visit if earlier, using grades shown in Table 13 below.

Table 13: Overall Tolerance

Grade	Score	Description
Excellent	0	No signs of irritation during the study
Good	1	Slight signs of irritation during the study, which resolved by the end of the study
Fair	2	Signs of irritation throughout the study
Poor	3	Subject discontinued due to irritation

Irritation was defined as any sign or symptom of intolerance.

Grades for Overall Tolerance will be summarized by treatment and overall.

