### 7.6 Safety Assessments

Safety assessments include vital signs, local cutaneous tolerance evaluation of the treated skin, and AEs. Vital signs (blood pressure and pulse) will be collected at each visit. A physical examination will be performed at Baseline (Day 1) and at Week 12. Urine pregnancy tests for all female subjects (regardless of childbearing potential) will be conducted at Screening and Baseline (Day 1) and at each subsequent visit. Adverse events will be collected by spontaneous reports from subjects (either verbal or recorded in the subject diary), by directed questioning of subjects, and by observation (see Section 8 for details about AEs). Adverse events, whether believed by the investigator to be related or unrelated to treatment, will be recorded on the eCRF.

At Visits 2 through 5 the investigator will assess local cutaneous tolerance by examining treated areas for clinically significant non-lesional erythema, peeling, and dryness that will be graded as shown below (Table 5, Table 6, Table 7) and recorded on the eCRF. Assessments will be recorded separately for the face and (if applicable) chest and/or back (including shoulders) for selected site(s). The investigator will also ask the subject if any stinging (Table 8), burning (Table 9), or itching (Table 10) has occurred on the face and chest and/or back (including shoulders), if applicable since the last visit (for Visit 2 in the last 2 weeks). Visit 2 assessments are made prior to first application. An AE should be recorded if the severity is worse than at Baseline. In addition, overall cutaneous tolerance should be graded at the Week 12 visit, or the last visit if earlier, using the grading shown in Table 11. The local cutaneous tolerance signs and

symptoms will be assessed separately for the face and chest and/or back (including shoulders), if applicable, for selected site(s), using the same scales below.

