### 8 ADVERSE EVENTS

Adverse events will be collected by spontaneous reports from subjects, either verbal or recorded in the subject diary, by directed questioning of subjects, and by observation.

The most common frequently reported adverse reactions during clinical trials with tazarotene cream 0.1% for the treatment of acne were desquamation, dry skin, erythema, and burning sensation, occurring in 10% to 30% of subjects. Adverse reactions occurring in 1% to 5% of treated subjects included pruritus, irritation, face pain, and stinging.

The investigator is to pay special attention at each visit to any signs of clinically significant dryness, non-lesional erythema, and peeling and report as an AE subsequent to the Baseline Visit if worse than at Baseline.

An AE is any untoward medical occurrence in a subject participating in a clinical trial. The event does not necessarily have to have a causal relationship with the study product. An AE can therefore be any sign, symptom, or disease, or any worsening of an existing sign, symptom, or disease, whether or not considered related to the study product or trial procedures, including injuries.

Any medical condition that is present at the time of Screening or Baseline should be considered as medical history and reported on the medical history eCRF and should not be reported as an AE except for AEs observed at the Baseline Visit due to study procedures performed at the Screening visit, which should be reported. Anticipated day-to-day fluctuations of pre-existing conditions should not be reported as AEs. Unexpected worsening of pre-existing conditions should be reported as AEs. The disease or condition being studied or expected progression,

signs, or symptoms of the disease or condition being studied such as worsening of acne should not be reported as an AE unless it is more severe than expected, results in discontinuation from the study or requires alternative therapy.

All serious adverse events (SAEs), all study product-related events, and all AEs leading to study product discontinuation must be followed until the clinical outcome is determined or until all attempts to determine resolution of the event are exhausted (not recovered is not an acceptable outcome for acute conditions). For other AEs, the status at the last visit can be entered into the eCRF.

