Table 14.2.2.1	Subject Compliance - Total Number of Applications, Number and Percentage of Subjects who are Compliant for the Baseline to Week 12 evaluation period	Safety	N/A	Unique
Table 14.2.2.2.1	Local Cutaneous Safety Evaluation by Treatment Group and Visit-Non-lesional erythema	Safety	N/A	Unique
Table 14.2.2.2.2	Local Cutaneous Safety Evaluation by Treatment Group and Visit-Peeling	Safety	N/A	Repeat
Table 14.2.2.2.3	Local Cutaneous Safety Evaluation by Treatment Group and Visit-Dryness	Safety	N/A	Repeat
Table 14.2.2.2.4	Local Cutaneous Safety Evaluation by Treatment Group and Visit-Burning	Safety	N/A	Repeat
Table 14.2.2.2.5	Local Cutaneous Safety Evaluation by Treatment Group and Visit-Stinging	Safety	N/A	Repeat
Table 14.2.2.2.6	Local Cutaneous Safety Evaluation by Treatment Group and Visit-Itching	Safety	N/A	Repeat
Table 14.2.2.3.1	Local Cutaneous Safety Evaluation by Treatment Group and Visit- Excluding Subjects with Signs or Symptoms at Baseline-Non-lesional erythema	Safety	N/A	Repeat
Table 14.2.2.3.2	Local Cutaneous Safety Evaluation by Treatment Group and Visit- Excluding Subjects with Signs or Symptoms at Baseline-Peeling	Safety	N/A	Repeat
Table 14.2.2.3.3	Local Cutaneous Safety Evaluation by Treatment Group and Visit- Excluding Subjects with Signs or Symptoms at Baseline -Dryness	Safety	N/A	Repeat
Table 14.2.2.3.4	Local Cutaneous Safety Evaluation by Treatment Group and Visit- Excluding Subjects with Signs or Symptoms at Baseline -Burning	Safety	N/A	Repeat
Table 14.2.2.3.5	Local Cutaneous Safety Evaluation by Treatment Group and Visit- Excluding Subjects with Signs or Symptoms at Baseline -Stinging	Safety	N/A	Repeat
Table 14.2.2.3.6	Local Cutaneous Safety Evaluation by Treatment Group and Visit- Excluding Subjects with Signs or Symptoms at Baseline -Itching	Safety	N/A	Repeat

Display Number	Title	Populations	Subgroup	Unique/ Repeat
Safety Tables				
Table 14.3.1.1	Overall Summary of Treatment Emergent Adverse Events	Safety	N/A	Unique
Table 14.3.1.2	Summary of Treatment Emergent Adverse Events by System Organ Class and Preferred Term	Safety	N/A	Unique
Table 14.3.1.2.1	Summary of Treatment Emergent Adverse Events by System Organ Class, Preferred Term and Severity	Safety	N/A	Repeat
Table 14.3.1.2.2	Summary of Treatment Emergent Adverse Events by System Organ Class, Preferred Term and Relationship to Study Drug	Safety	N/A	Repeat

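### The tolerability score tables do not show how many subjects worsened from their own Baseline grade; add a worse-than-Baseline count and a shift table, and define the exclusion summary as same-item

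*SAP*

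**What the plan says.** SAP 3.2.1 lists the local cutaneous evaluation (dryness, non-lesional erythema, peeling, stinging, burning, itching) among the primary safety endpoints, beside treatment-emergent adverse events (TEAEs).

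SAP 9.2 and protocol 11.5.2 plan two summaries of the scores:

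- **Full summary.** The "scores will be summarized by treatment group and visit including sample size, frequency count and percentage for each visit". In the display list these are Tables 14.2.2.2.1 to 14.2.2.2.6, one per item, in the safety population, for example "Local Cutaneous Safety Evaluation by Treatment Group and Visit-Non-lesional erythema".
- **Exclusion summary.** "A similar summary will be provided excluding subjects with signs or symptoms present at Baseline." These are Tables 14.2.2.3.1 to 14.2.2.3.6, again one per item, for example "Excluding Subjects with Signs or Symptoms at Baseline-Non-lesional erythema" and "Excluding Subjects with Signs or Symptoms at Baseline-Peeling".

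The Baseline grades exist for this purpose. Protocol 7.6 states that "Visit 2 assessments are made prior to first application" and uses the same 0 to 3 scales at Visits 2 to 5. The same section treats worsening as the event of interest: "An AE should be recorded if the severity is worse than at Baseline".

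Neither the text nor the display list contains a change score, a count of subjects worse than Baseline, a worst post-baseline grade or a shift table for these six items.

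**The concern.** A reader of the study report will want to know how many subjects developed irritation, or had it get worse, on each product. The full summary mixes signs that were already present with signs that appeared on treatment. The exclusion summary shows new irritation only in subjects who were clear at Baseline, so a subject who goes from mild to severe is absent from it. In the full table that subject is a severe score with no link to the starting grade.

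The plan makes this link elsewhere. SAP 6.7.3 defines change from Baseline on matched pairs, SAP 9.6 applies it to vital signs, and Table 14.3.2 plans a change display for the physical examination. Both of those are secondary endpoints; the primary scores get nothing comparable. The study is explicitly unpowered and exists to estimate comparative tolerability (protocol 11.1, SAP 4.3), so a clear estimate of irritation on treatment is its main product.

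A second problem is that the exclusion rule is not defined. The wording does not say whether a table drops subjects with that item at Baseline or subjects with any of the six. Two programmers could produce different denominators for the same table.

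**Working it through.** **Inputs.** The arm sizes are 50/50/25/25 (protocol 6.4). They reproduce: 150 × 2/6 = 50 and 150 × 1/6 = 25. They are approximate, because about 8 subjects aged 9 to 11 go 1:1 to the lotion arms only: 142 × 2/6 + 4 = 51.3, 142 × 2/6 = 47.3, 142/6 + 4 = 27.7 and 142/6 = 23.7. This does not affect what follows. There is no power calculation to reproduce. The documents give no Baseline prevalence for any item, so q below is an assumption, and the score distributions are invented for illustration.

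**1. Can the full table give the number who worsened?** Take n = 50, with 35 none and 15 mild at Baseline, and the same 35/15 at a later visit.

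- Minimum worsened: 0 (nobody changed).
- Maximum worsened: 15 (all 15 later mild scores came from none, and the 15 who were mild went to none).

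Identical tables therefore fit any count from 0 to 15.

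**2. A later visit with visible irritation.** Same Baseline; later visit 30 none, 10 mild, 5 moderate, 5 severe.

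- At least 10 worsened, since nobody started above mild and 5 + 5 = 10 are now moderate or severe.
- At most 20 worsened, everyone now above none (10 + 5 + 5).
- Mild to severe: from max(0, 15 + 5 − 50) = 0 to min(15, 5) = 5.

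**3. Do the two summaries together settle it?** Under a same-item rule, and if visit denominators match, subtracting the exclusion table from the full table isolates the subjects who had the item at Baseline. Suppose these are 15 subjects, 10 mild, 4 moderate and 1 severe, who later score 5 none, 4 mild, 2 moderate and 4 severe.

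- At least 3 worsened, since at most 1 of the 4 severe scores was severe already.
- At most 6 worsened (2 moderate plus 4 severe; nobody in this group can worsen into mild).
- Mild to severe: from max(0, 10 + 4 − 15) = 0 to min(10, 4) = 4.

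Had all 15 been mild at Baseline, the answer would be exactly 6. Subtraction narrows the range but does not generally close it. Under an any-item rule it does not isolate this group at all.

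**4. What the exclusion costs.** Subjects kept per active arm are 50(1 − q) under a same-item rule and 50(1 − q)^6 under an any-item rule with independent items. The 95% half-width for a difference between two equal arms is 1.96 × √(2p(1 − p)/n), with p = 30%, the top of the 10% to 30% range that protocol section 8 gives for the commonest reactions to tazarotene cream.

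| Summary | Assumed q | Kept of 50 | Half-width (points) |
|---|---|---|---|
| All assessed subjects | any | 50 | 18.0 |
| Same-item exclusion | 10% | 45 | 18.9 |
| Same-item exclusion | 20% | 40 | 20.1 |
| Any-item, independent | 10% | 27 (26.6) | 24.6 |
| Any-item, independent | 20% | 13 (13.1) | 35.1 |

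If the items always occurred together, the any-item rule would keep the same 45 and 40 as the same-item rule. Positive correlation gives values in between.

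**The case against.** The strongest defence is that worsening is already captured as adverse events. Protocol 7.6 asks for an AE when severity exceeds Baseline. Protocol section 8 tells the investigator to "report as an AE subsequent to the Baseline Visit if worse than at Baseline" for dryness, erythema and peeling. SAP 9.3.1.2 counts pre-existing events that worsen after dosing as TEAEs, and TEAEs are themselves a primary endpoint, tabulated by maximum severity. A severe score also still appears in the full table. The two summaries are a coherent descriptive pair for an unpowered study, with Baseline signs balanced by randomization in expectation.

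Much of this stands, and it rules out saying that worsening is hidden. But the AE route is a partial substitute, and it is weakest for subjects who had signs at Baseline:

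- Section 8 refers to clinically significant signs, treats conditions present at Baseline as medical history, and exempts expected daily fluctuation of existing conditions.
- AE severity (protocol 8.3.1) is graded by interference with activity, not on the 0 to 3 sign scales.
- Intermittent AEs can be recorded once (protocol 8.2), so the course by visit is lost.
- Protocol 11.5.3 defines TEAEs by onset on or after first dosing and omits worsening; the SAP includes it.

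The overall tolerance grade (SAP Table 13) is a single global rating, neither item-specific nor referred to the Baseline grade.

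A reader might also infer that Baseline signs are dealt with by deleting subjects, so that the primary endpoint loses much of its sample. The documents do not support that. The exclusion summary is additional, and the full summary loses nobody to it.

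**Conclusion.** The point holds in a limited form. The score tables for a primary endpoint contain no within-subject comparison with Baseline, although the data for one are collected, and the two planned summaries do not in general identify how many subjects worsened (0 to 15 of 50 in the simplest example). This is a free improvement, not an error that invalidates the planned tables.

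Two stronger readings should be resisted. First, it is tempting to say that mild itching at Baseline removes a subject from the peeling and erythema tables. The wording permits that, but one table per item fits a same-item rule equally well, and the documents do not choose. Second, a large loss of subjects cannot be asserted. It needs the any-item reading, an assumed prevalence and near-independence of signs that may well occur together. Under a same-item rule at 10% to 20% the loss is 5 to 10 of 50, in a supplementary table only. Eligibility rules (no interfering facial skin disease, 14 days off topical acne treatments) may make Baseline signs less common still.

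**What to change.** In SAP 9.2, add for each of the six items, in all safety-population subjects with a Baseline and a post-baseline score:

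1. the number and percentage whose score is higher than their own Baseline score, at each visit and at the worst post-baseline score;
2. a shift table of Baseline grade by worst post-baseline grade. This also shows subjects already severe at Baseline, who cannot score higher.

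Keep face and chest/back results separate, as SAP 3.2.1 does. Keep Tables 14.2.2.3.1 to 14.2.2.3.6, because protocol 11.5.2 promises that summary and dropping it would depart from the protocol. State that each of these tables excludes only subjects with that same item present at Baseline. While the shells are open, give Table 14.2.2.2.1 and its repeats the counts and percentages that SAP 9.2 describes; the current shell has only score and severity columns.

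The cost is a short SAP revision and some extra programming. No new data, visits or assessments are needed.

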9.3. Adverse Event (AE)

9.3.1. Adverse Event Definitions

The following definitions will apply to the reporting of adverse events.

9.3.1.1. Adverse Event (AE)

An adverse event (AE) is any untoward medical occurrence in a subject participating in a clinical trial. The event does not necessarily have to have a causal relationship with the study product. An AE can therefore be any sign, symptom, or disease, or any worsening of an existing sign, symptom, or disease, whether or not considered related to the study product or trial procedures, including injuries.

Any medical condition that is present at the time of Screening or Baseline should be considered as medical history and reported on the medical history eCRF and should not be reported as an AE except for AEs observed at the Baseline Visit due to study procedures performed at the Screening visit, which should be reported. Anticipated day-to-day fluctuations of pre-existing conditions should not be reported as AEs. Unexpected worsening of pre-existing conditions should be reported as AEs. The disease or condition being studied or expected progression, signs, or symptoms of the disease or condition being studied such as worsening of acne should not be reported as an AE unless it is more severe than expected, results in discontinuation from the study or requires alternative therapy.

9.3.1.2. Treatment-Emergent Adverse Event (TEAE)

A treatment-emergent adverse event (TEAE) is defined as any AE which started on or after the first administration of study drug and include those events started prior to the first administration of study drug but which worsened after the first administration of study drug.

9.3.1.3. Serious Adverse Event (SAE)

A serious adverse event (SAE) is any AE occurring at any dose that results in any of the following outcomes:

- 1. Death
- 2. Life-threatening (subject at immediate risk of death)
- 3. Inpatient hospitalization or prolongation of hospitalization
- 4. Results in persistent or significant disability/incapacity
- 5. Results in congenital anomaly/birth defect

Important medical events that may not result in death, are not life-threatening, or do not require hospitalization may be considered an SAE when, based upon appropriate medical judgment, they may jeopardize the subject and may require medical or surgical intervention to prevent one of the outcomes listed above. Examples of such medical events include allergic bronchospasm requiring intensive treatment in an emergency room or at home, blood dyscrasias or convulsions that do not result in inpatient hospitalization, or the development of drug dependency or drug abuse.

9.3.2. Assessment of Adverse Events

9.3.2.1. Severity of an Adverse Event

The severity of an adverse event was classified into one of three categories:

- 1. Mild (Grade 1): Awareness of sign or symptom, but easily tolerated. Not likely to interfere with normal activity or require medical attention.
- 2. Moderate (Grade 2): Discomfort enough to cause interference with usual activity. May require medical intervention
- 3. Severe (Grade 3): Incapacitating such that normal activity is prevented. Likely requires medical intervention and/or close follow-up.

9.3.2.2. Relationship to Study Product (Causality)

The degree of "relatedness" of the AE to the study product was described using the following categories:

- 1. Not Related: The event is clearly due to extraneous causes (e.g., diseases, environment, etc.). Specify if known. Or, the event is most probably produced by other factors such as the subject's clinical state, therapeutic interventions, or concomitant therapy and does not follow a known response pattern to the study product.
- 2. Possibly Related: The event is temporally related to study product use but can be explained by another etiology. Information on the effect of study product withdrawal may be lacking.
- 3. Probably Related: The event is temporally related to study product use and is consistent with known effects of the study product and/or improves upon withdrawal of the study product.

4. Definitely Related: The event follows a reasonable temporal sequence from the time of study product administration and/or follows a known response pattern to the study product, and could not have been produced by other factors such as the subject's clinical state, therapeutic intervention, or concomitant therapy, and either occurs immediately following study product administration or improves on stopping the product, or there is a positive reaction at the application site.

